Project Title: Airway Clearance for Pediatric and Adult Cystic Fibrosis Patients Using a Portable Intra-Pulmonary Percussion Device

Investigator(s): [name], [name], [name], [name], [name].

Abstract:

Airway clearance has a crucial role in the prevention of progression of lung disease in cystic fibrosis patients. Despite multiple options available for airway clearance, frequently cystic fibrosis patients have difficulties performing regular airway clearance in an at-home environment. We will compare pulmonary function testing and patient satisfaction with their current home device compared to the portable internal airway percussion device proposed (PIAPD). Our hypothesis is that there is no difference in pulmonary function testing after using PIAPD comparing to their home device. Our goal is to provide an equally effective, less expensive, alternative airway clearance technique for cystic fibrosis patients.

Background:

Cystic Fibrosis (CF) is an autosomal recessive disease that affects more than 30,000 people in the United States and more than 70,000 worldwide. The abnormal Cystic Fibrosis Transmembrane conductance regulator (CFTR) function leads to multiple organ manifestations. In the lungs, the dysfunctional CFTR mutation leads to abnormal thick, sticky mucus in the airways that traps microorganisms, leading to infections, inflammation and respiratory failure, which are the main causes of death in CF patients. Daily airway clearance plays a key role in preventing lung function deterioration in CF. Typically, a CF patient gets airway clearance therapy at least two times daily, each session lasting for about 30 minutes. There are different types of airway clearance therapies. Some of them are active, requiring patient cooperation and some coordination of breathing, while others are predominantly passive. In the United States, the most commonly utilized technique is high frequency chest wall oscillation, more commonly known as “the VEST”. This vibration loosens secretions in the bronchi that the patient will have to actively expel. The apparatus of vest therapy involves a wearable jacket, a hose pipe and an air compressor. This apparatus requires electric supply from the mains and is not portable.

Vibrations can also be applied internally to airways through a mouthpiece. The existing devices that apply internal airway vibration include: Positive Expiratory Pressure Therapy (PEP), Flutter Valve therapy (Flutter) & Intrapulmonary Percussive Ventilation (IPV). PEP & flutter therapy involve portable, handheld devices without the need for electrical power. However, they both need patients' active participation and they are only active during patients' expiration phase of breathing. IPV is a modified ventilator that delivers pulses of air under pressure into airways. The equipment requires electricity and is not portable. IPV is only used within the hospital settings.

Studies comparing different modes of airway clearance therapies have shown that they are all comparable to each other when used properly. A portable “Internal Airway Percussion” (PIAP) device that can deliver internal vibration to the airways both during inspiration and expiration and that requires patients' minimal cooperation would in theory be superior to existing devices. High frequency oscillation (HFO) of bronchial airway surface liquid (ASL) is an experimental technique developed at UF for the transmission of high-frequency square form sound waves superimposed on normal breathing through a mouthpiece and into the airways. In this pilot study, we propose to test HFO as a means of airway clearance therapy in CF patients.

If the PIAP device is non-inferior to the SOC device, it would provide CF patients several advantages. The current VEST therapy, which is SOC for airway clearance, can cost anywhere from \$5,000 to \$20,000 for some of the newer models. The device under study could be made and provided to patients at a fraction of this cost. Furthermore, patients with CF are extremely vulnerable to respiratory infections and complications arising from such. In the time of COVID-19, this portable system can be used in the patient's home and carried with them wherever they go. This provides a highly portable as well as cost-effective option for airway clearance which will allow them to have greater flexibility where airway clearance is performed and allow them greater freedom to pursue activities that they enjoy.

The PIAP device,(as pictured in Figure 4) that we have developed has been previously tested in several IRB-02 approved pilot studies here at the University of Florida by [name] in a population of healthy volunteers. Published results of these studies report this device's waves produce vibrations within the airways, loosening Airway Surface Liquid (ASL), enhancing airway clearance and decreasing the sense of breathing effort. Furthermore, the IAP device was found to painlessly increase exhalation of intra airway molecules and droplets in healthy individuals.

For this study, we would like to test this unique, custom designed, inexpensive, portable IAP device (PIAPD) as a comfortable alternative for airway clearance in CF patients.

Specific Aims:

1. To determine if Portable Internal Airway Percussion Device (PIAPD) is a non-inferior at-home method of airway clearance in patients with CF, we will compare changes in pulse oximetry and forced expiratory volume in one second (FEV1) prior to and 2 hours after airway clearance performed with standard airway clearance devices vs. the PIAPD. The primary endpoint will be a comparison of results of the aforementioned pulmonary function testing between the two devices.
2. Secondary endpoints include will include comparison of patient satisfaction (tolerability and acceptability) with standard airway clearance devices and PIAPD.
3. We will measure CF patient perception of breathing effort and device use for both methods.

Study Design: This is a pilot study where we aim to compare initial use of the standard airway clearance device (SACD) (as pictured in Figure 2) with subsequent use of a PIAPD in patients ages 6-21 years with stable CF. Our primary hypothesis, stated as Null, is that there is no effect of on FEV1 2 hours after use and there is no effect on perception of effort and efficacy for the PIAPD device.

General Inclusion Criteria:

- Ages 6-21 years
- Stable CF as determined by pulmonary physician assessment
- Assents to forego additional experimental treatments during the study
- Currently using and familiar with airway clearance therapy for treatment of CF
- Participant (or parent or legal guardian if the participant is a minor) is willing to provide Informed Consent

General Exclusion Criteria:

- FEV1 < 40% predictive
- Pneumothorax
- Hemoptysis

- COVID-19 diagnosis within last 14 days
- Non-compliance
- Inability to obtain informed consent
- Any condition that, in the opinion of the investigator, would interfere with the study conduct or the safety of the participant

Additional Exclusion Criteria: Outpatient Arm (in addition to general exclusion criteria above)

- Decrease in FEV1 > 10% from baseline over last 12 months
- Antibiotic Initiation for acute CF exacerbation
- Hospitalization for CF Exacerbation

Additional Exclusion Criteria: Inpatient Arm (in addition to general exclusion criteria above)

- Failure to increase FEV1 $\geq 10\%$ from initial PFTs on admission by day 9 of hospitalization.

Our patients will be recruited from our CF outpatient Clinic and from our CF inpatient population. Participants will be randomly assigned to perform airway clearance with the Standard Airway Clearance device (SACD) or Portable Internal Airway Percussion device (PIAPD). A large majority of our patients will be using VEST therapy as their standard of care airway clearance. A few might be using an Intrapulmonary Percussion Device that uses a mechanism different from the device we will be testing. Based on past experience, it is unlikely that this will present a significant source of variability.

After discussing the study with a prospective participant and obtaining informed consent, participants will be randomized to either the standard of care or experimental group:

Outpatient arm:

On day 1, baseline FEV1 as measured on Smart One® portable home spirometer (Figure 1) and pulse oximetry will be obtained before and 2 hours after airway clearance, either performed with SACD method, PIAPD at 15hz. The frequency of the device will stay at 15 hz for the duration of the study as it has been previously shown to be the most effective frequency for better airway clearance (i.e., getting deeper into the airways). Participants will also be asked to give a rating of breathing effort using a Modified Borg Dyspnea Scale.

For the next two weeks, airway clearance therapy, either performed with SACD method or PIAPD, will be performed by the patient daily (CF patients perform airway clearance daily as part of standard of care for their disease). Spirometry/pulmonary function testing will be collected twice per week over the two-week period with a pre and post FEV1, pulse oximetry, and rating of breathing effort. This testing will be done via telemedicine so that the PI or co-investigator can assist the patient with the PIAPD if necessary and conduct the testing in a safe and efficacious manner. At the end of the two weeks, the participant will be asked to complete a short survey regarding the ease of use and acceptability of the airway clearance device they had been using for the first part of the study.

At the end of the initial 2-week period, the patient will be crossed-over to the other arm of the study and the same procedures will be repeated as per the above procedures. At the end of the study, patients will return the PIAPD device to the study team.

FIGURE 1

Figure 1: Smart One® portable home spirometer is the standard of care for at-home measurement of FEV-1.

Inpatient arm:

Patients who are admitted to the hospital for a normal seasonal disturbance of their CF are admitted, as SOC, for a 14-day in-patient stay. When patients are admitted, they bring their VEST system, as this is the standard of care device used by over 95% of CF patients for airway clearance therapy. Following admission, patients will be informed of the study by the PI or one of the designated co-investigators. All study procedures will be explained and ample time to ask questions will be allotted. If the patient agrees to participate written informed consent will be obtained and the following procedures performed:

Hospital Stay Days 1-3: Patients will only use their SOC airway clearance therapy. This will allow for a “wash-out period” providing all the patients with good airway clearance prior to collecting data (some patients may have had poor compliance prior to hospitalization). The participant will also be asked to complete a short survey regarding the ease of use and acceptability of their SOC airway clearance device, at the end of this 3-day wash-out period. Furthermore, during this period, we will get daily spirometry with a portable spirometer once per day after first airway clearance of the day, along with pulse oximetry.

Hospital Stay Day 4: If, in the judgement of the PI, the participant has stabilized, we will randomize them to use either their SOC device or the study device. On Day 4, patients will be randomized to SOC or the new airway clearance device. We will collect the patient’s ratings of breathlessness with the Modified Borg Dyspnea Scale and perform spirometry again with the Smart One® portable spirometry device before and two hours after airway clearance procedures for the first airway clearance of the day. We will also obtain pulse oximetry.

Hospital Stay Day 5: we will alternate the modality for the first airway clearance session of the day (using whichever device they were not randomized to use on Day 4), repeating the Modified Borg Dyspnea Scale and performing spirometry again before and two hours after airway clearance along with pulse oximetry. At this point, they will have used both the airway clearance devices, and they will be asked to complete a short survey regarding the ease of use and acceptability of the study airway clearance device.

Hospital Stay Days 6-9: we will continue with daily spirometry, dyspnea measurements and pulse oximetry once per day after the first airway clearance of the day using the study device.

Hospital Stay Days 10-14: patients who have increased their FEV1 by at least 10% from admission by day 9 of hospitalization and whose symptoms have clinically improved, will be given the choice of whether to use their SOC device or the experimental study device. Whichever device they choose, they will use for two airway clearance sessions, along with dyspnea measurements, and pulse oximetry on days 10-14 of hospitalization.

At the end of the two weeks, the participant will be asked to complete a short survey regarding the ease of use and acceptability of each airway clearance device they had been using for the study. At the end of the study, we will ask that the patient return the experimental device to the study team.

FIGURE 2

Figure 2: The Vest® Airway Clearance System is the standard of care for airway clearance in both adult and pediatric

Safety Endpoints:

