We shall cross-tabulate the pre- and post-treatment spirometry measures for study condition and group. Significance for association will be obtained by repeated measures ANOVA. The false positive and false negative rates will be estimated by exact binomial confidence limits. This is a pilot study that is seeking a promising outcome as opposed to a definitive one. We shall consider the result as promising if (a) no false positives occur and (b) the false negative rate is below 50%.

Power/Sample Size: The study will have a goal to recruit 50 CF (10 inpatient and 40 outpatient) patients. Initial data analysis to be completed after the first 25 patients have completed each test condition.

Measurable outcomes and expected timeline: We expect the PIAPD is equal to standard airway clearance in CF patients. We expect PIAPD will decrease the sense of breathing effort and increase patient sense of efficacy.

Compliance/Accountability/Regulatory

Statement of Compliance

This study will be conducted in compliance with the protocol and will be generally consistent with current Good Clinical Practices (GCP), adopting the principles of the Declaration of Helsinki and all applicable regulatory requirements (ICH E6, 45CFR46, and FDA 21CFR sections 11, 50, 56, 312).

Prior to study initiation, the protocol and the informed consent documents will be reviewed and approved by UF's Institutional Review Board (IRB). Any amendments to the protocol or consent materials will be approved before they are implemented.

Adverse Event Reporting and Safety Monitoring

In the event of an adverse event the following definitions and processes will be used/followed:

Adverse Event Definitions

In this clinical research study, an adverse event (AE) is any occurrence or worsening of an undesirable or unintended sign, symptom or disease that is associated with study procedures. As an observational study, AEs occurring between study visits will not be reported unless deemed associated with study procedures. Throughout the study, the investigator must record AEs related to study procedures on source documents regardless of severity.

Unexpected Adverse Event

An AE is considered unexpected when the nature (specificity) or severity of the event is not consistent with the risks described in the protocol or informed consent document for specific protocol-required interventions.

Grading Adverse Event Severity

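### Aim 1 infers non-inferiority from a 2-hour FEV1 change that the plan never shows, or requires, the standard device to move

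*Combined protocol and SAP*

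**What the plan says.** The goal in Specific Aims, item 1, is "To determine if Portable Internal Airway Percussion Device (PIAPD) is a non-inferior at-home method of airway clearance in patients with CF". The measure is the change from before a session to two hours after it: "we will compare changes in pulse oximetry and forced expiratory volume in one second (FEV1) prior to and 2 hours after airway clearance".

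The hypotheses are differently worded. The Abstract has "Our hypothesis is that there is no difference in pulmonary function testing after using PIAPD comparing to their home device". Study Design has "Our primary hypothesis, stated as Null, is that there is no effect of on FEV1 2 hours after use". Under the heading on measurable outcomes the plan adds "We expect the PIAPD is equal to standard airway clearance in CF patients".

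The evidence offered for airway clearance is of two kinds. One is long-term: "Daily airway clearance plays a key role in preventing lung function deterioration in CF" (Background). The other compares active methods with each other: "Studies comparing different modes of airway clearance therapies have shown that they are all comparable to each other when used properly" (Background). Earlier work on the study device was in healthy volunteers. None of this gives a 2-hour FEV1 change for a standard device.

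Eligibility requires "Stable CF as determined by pulmonary physician assessment" and current use of airway clearance. The recruitment goal is 10 inpatients and 40 outpatients. The only conditions are SACD and PIAPD. The Statistical Analysis section cross-tabulates pre and post spirometry by condition and group, tests by repeated measures ANOVA, and calls the result promising on a rule about false positives and false negatives. It states no margin.

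**The concern.** Similarity to a comparator is evidence of efficacy only if the comparator itself moves the endpoint in the trial at hand. Here that is left open. Participants are clinically stable and already clear their airways daily, so the acute gain from one more session could be small. The FEV1 rise of at least 10% that the inpatient arm refers to is measured from admission to day 9, not across one session, so it does not fill the gap. Pulse oximetry, also named in Aim 1, has no stated SACD effect either.

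If the SACD change is near zero, every device looks alike, including one that does nothing. The analysis is a difference test and the hoped-for result is no difference, so an uninformative comparison would read as success. At stake is describing an ineffective device as equal to a daily therapy that the protocol itself treats as protective, in patients aged 6 to 21.

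**Working it through.** **The plan's own figure.** The recruitment goal of 50 can be checked only as 10 + 40 = 50. No alpha, power, margin, SD or expected effect is given, so it cannot be re-derived.

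**Inputs from the documents.** There are 40 outpatients in a two-period crossover, so the device comparison is paired. Tests per device: one on day 1 plus two a week for two weeks, 1 + 2 × 2 = 5. The 2-hour interval is spelled out only for day 1, so five 2-hour tests is a reading. The 10 inpatients have one pre and 2-hour post session per device (days 4 and 5) and are left out.

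**Assumptions, because the documents give no figure** (points of FEV1):
- e, the true SACD change: 0 to 3. An inert PIAPD has true change 0, so the true difference (PIAPD minus SACD) is −e.
- M, an illustrative margin: 3.
- SDd, the SD of the paired device difference, from two sets of assumptions. (a) A single-session change has SD 4, 6 or 8, five independent tests are averaged, and device effects do not vary by patient: SE = √(2·SD²/(5·40)) = 0.40, 0.60, 0.80, which equals SDd 2.5, 3.8, 5.1. (b) SDd is set at 5, 8 or 10, which allows for correlated or fewer tests and patient-by-device variation: SE = SDd/√40 = 0.79, 1.26, 1.58.

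**Formulas for an inert PIAPD.**
- Non-significant at two-sided 0.05: Φ(1.96 − e/SE) − Φ(−1.96 − e/SE).
- Passes non-inferiority: Φ((M − e)/SE − 1.96).

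**Example**, SDd 8. With e = 0: 3/1.265 − 1.96 = 0.41, and Φ(0.41) = 66%. With e = 1: Φ(1.169) − Φ(−2.751) = 88% non-significant. The noncentral t gives 64% and 88%.

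| SDd | SE | e=0 non-sig. | e=0 passes | e=1 non-sig. | e=1 passes | e=2 non-sig. | e=2 passes |
|---|---|---|---|---|---|---|---|
| 2.5 | 0.40 | 95% | >99% | 29% | >99% | <1% | 71% |
| 3.8 | 0.60 | 95% | >99% | 62% | 92% | 8% | 38% |
| 5.1 | 0.80 | 95% | 96% | 76% | 71% | 29% | 24% |
| 8 | 1.26 | 95% | 66% | 88% | 35% | 65% | 12% |
| 10 | 1.58 | 95% | 48% | 90% | 24% | 76% | 9% |

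SDd 5 is almost the same as the 5.1 row. Two results need no assumed SD. At e = 0 the non-significant rate is 95% at any sample size. When M = e, the pass rate is Φ(−1.96) = 2.5%. False non-inferiority is therefore held to 2.5% or less only if the margin is no larger than the true SACD effect, and the plan gives neither.

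**Does requiring the SACD interval to lie above zero help?** Simulated under assumptions (a), with M = 3 and the SE of the SACD mean equal to SD/√200. Share of trials in which an inert PIAPD clears both the SACD check and non-inferiority:

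| Scenario | SD 4 | SD 6 | SD 8 |
|---|---|---|---|
| SACD effect 0, no drift | about 2.5% or less | about 2.5% or less | about 2.5% or less |
| Both devices inert, +1 point drift in both conditions | 94% | 65% | 39% |
| SACD effect +1, no drift | 94% | 57% | 19% |
| SACD effect +2, no drift | 71% | 38% | 19% |

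The check removes the worst case. It does not deal with drift, or with a margin wider than the SACD effect.

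**The case against.** The strongest reply is that this is a pilot seeking a promising rather than a definitive result, with no margin and no non-inferiority test, so the missing test is the root defect and this point is downstream of it. That stands in part. It limits the consequence, and it means that the pass rates above illustrate a test the plan does not contain. It does not remove the gap: Aim 1 still states a non-inferiority determination, and without a margin the likely route to error is a non-significant ANOVA read as equality.

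A reader might infer more than the documents support:
- *That the plan never looks at the SACD change.* It does. Pre and post FEV1 are collected on the SACD and tabulated by condition. What is missing is an estimate, an interval and a consequence.
- *That comparability among active devices is the only support cited.* The Background also cites prevention of long-term decline, and the text cites published results for the study device. Neither bears on 2-hour FEV1 with a standard device.
- *That no margin could help.* A margin no larger than the true SACD effect does control the error.
- *That an inert device would almost always pass a 3-point margin.* That holds only for the smaller SDs. With SDd 8 to 10 and no SACD effect, the rate is 66% to 48%.

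**Conclusion.** The point holds. The plan seeks non-inferiority or equality on an endpoint for which it states no SACD effect, has no untreated reference, and ties no conclusion to the SACD's own change. With a true SACD change of zero, an inert PIAPD is non-significant 95% of the time. With an assumed 3-point margin and 40 outpatients, it would pass non-inferiority about 48% to over 99% of the time for SDd from 10 down to 2.5. At an SACD effect of +1, the figures are 29% to 90% non-significant and 24% to over 99% passing. SD, margin and effect are all assumed.

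It would go too far to say that the plan contains a rule that formally declares an inert device non-inferior. It would also go too far to treat an SACD interval above zero as proof of assay sensitivity: without an untreated session, time-of-day and repeat-test effects remain in that change. The point should be acted on, but pilot status keeps it short of a fatal flaw.

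**What to change.** Add to the Statistical Analysis section:

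> The pre-to-2-hour FEV1 change will be estimated with a 95% CI for the SACD and for the PIAPD. If the SACD interval does not lie above zero, no conclusion of equality or non-inferiority will be drawn, and the comparison will be reported as uninformative about efficacy. If it does lie above zero, this is a necessary but not sufficient condition, because without an untreated session the change cannot be separated from time-of-day or repeat-test effects. Any non-inferiority margin must be no larger than a justified SACD effect; otherwise the result will be described as a difference with its CI, not as non-inferiority.

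This costs some wording and two estimates from data already collected, with no new visits. A usable margin would need a sourced SACD effect, which the documents do not supply. Without one, the non-inferiority wording in Aim 1 should give way to estimation. The downside is that the verdict may become inconclusive.

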This study will utilize the National Cancer Institute (NCI) Common Toxicity Criteria for Adverse Events (CTCAE Version 3.0) to classify AE severity.

All AEs Grade 2 or greater pertaining to study procedures will be recorded on the UF IRB adverse event log, which will be reviewed by the IRB annually at continuing review. The investigator will make a determination as to the relation to participation in the study. Events will be assessed and reported in accordance with the ICH Guidelines for Good Clinical Practice and per the guidance of the DHHS Office for Human Research Protections (OHRP). Should there be an adverse event or unanticipated problem that is both serious and unexpected it will be evaluated by the PI and reported to the IRB as appropriate per current regulatory guidelines.

Informed Consent

Participants will sign their own informed consent form (or in the case of parents, they will consent for their child). This study will require written assent from minors. This study does not allow for use of legally authorized representatives or LARs. Each participant will receive a signed copy of their informed consent for their records. Participants will have the opportunity to ask questions before they sign the consent form and when a study coordinator calls them to confirm their information.

Risks and Benefits

Aside from the normal shortness of breath, which is expected as part of doing standard of care airway clearance and pulmonary function testing, there are no discomforts or risks associated with study that we know of. This research study may also include risks that are unknown at this time. If the portable airway device works as well as the standard airway clearance device, it will potentially provide a less expensive, portable alternative for patients with CF that they can use in their homes without coming to clinic and during telemedicine visits with their physician.

It is also possible, that patients may not see an improvement and may even see a worsening of their airway clearance as measured by FEV-1 while using the experimental device.

Confidentiality

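### Aim 1's 2-hour change cancels any fall in FEV1 that builds up over two weeks of home use, and no listed endpoint compares FEV1 level between devices over that period

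*Combined protocol and SAP*

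**What the plan says.** The conclusion sought is broad. Specific Aims, Aim 1: "To determine if Portable Internal Airway Percussion Device (PIAPD) is a non-inferior at-home method of airway clearance in patients with CF". The measure is narrow: FEV1 and pulse oximetry are compared "prior to and 2 hours after airway clearance performed with standard airway clearance devices vs. the PIAPD", and "The primary endpoint will be a comparison of results of the aforementioned pulmonary function testing between the two devices". Study Design states the primary null as "there is no effect of on FEV1 2 hours after use". The secondary aims cover satisfaction, breathing effort and device use, not FEV1 over time.

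The outpatient arm uses each device daily for two weeks: "At the end of the initial 2-week period, the patient will be crossed-over to the other arm of the study". Besides the day-1 readings, spirometry "will be collected twice per week over the two-week period with a pre and post FEV1". No washout between the two outpatient periods is described.

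Statistical Analysis tabulates spirometry before and after treatment by condition and group and names a repeated measures ANOVA. It gives no visit term, contrast or non-inferiority margin. Safety Endpoints uses a drop of more than 10% from baseline FEV1 as a criterion for ceasing use of the experimental device in an individual patient. Risks and Benefits acknowledges that patients "may even see a worsening of their airway clearance as measured by FEV-1 while using the experimental device".

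**The concern.** An at-home airway clearance method has two effects of interest: what one session does, and whether regular use holds lung function over time. The Background section gives the second as the reason for daily clearance. Aim 1's measure addresses only the first. Each session's pre value is subtracted from its own post value, so a patient whose FEV1 drifts down over the two weeks contributes the same change as one who stays level, provided the session gain is the same.

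The blind spot favours the new device. If the PIAPD held FEV1 less well than standard clearance over two weeks, the comparison behind the at-home conclusion would not be built to show it, although the protocol names worsening FEV1 as possible and already collects the readings.

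**Working it through.** **Plan's own figure.** The sample size is 10 inpatients + 40 outpatients = 50. No SD, effect size, power, alpha or margin accompanies it, so there is no calculation to reproduce.

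**Inputs from the documents.** 40 outpatients; two weeks on each device; pre and post FEV1 on day 1 and twice a week, so 1 + 2 × 2 = 5 measured sessions per period if day 1 is additional. Inpatients have before-and-after readings only on days 4 and 5, so the point concerns the outpatients.

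**Assumptions (not in the documents).** Measured days 1, 4, 7, 10 and 14; FEV1 in percentage points; patient-by-period SD 3, constant within a period; independent error SD 5 on each reading; a linear fall on the PIAPD only; equal session gain on both devices; no carry-over; paired t interval with 39 df (t = 2.023).

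**Step 1: cancellation.** Let L(t) be the underlying level and g the session gain. Then pre = L(t), post = L(t) + g, and post − pre = g, whatever L(t) does. With equal g, the expected device difference is 0 for a fall of any size. This step needs none of the assumed SDs.

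**Step 2: what an averaged level would show.** The share of the fall reached on the five days is 0/13, 3/13, 6/13, 9/13 and 13/13, with mean 31/65 = 0.477. A 5-point fall appears as 2.4 points and a 3-point fall as 1.4. Over the two week-2 visits the mean share is (9 + 13)/26 = 0.846, giving 4.2 and 2.5 points.

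**Step 3: precision.** Half-width = 2.023 × SD / √40.

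| Comparison, PIAPD minus SACD | Variance of paired difference | SD | 95% half-width | Size of difference, 5-point fall |
|---|---|---|---|---|
| 2-hour change, mean of 5 sessions | 2 × 50/5 = 20 | 4.47 | 1.4 | 0 |
| Level, mean of all 10 readings | 2 × (9 + 25/10) = 23 | 4.80 | 1.5 | 2.4 |
| Week-2 pre-session, unadjusted | 2 × (9 + 25/2) = 43 | 6.56 | 2.1 | 4.2 |
| Week-2 pre-session, day-1 value as covariate | 43 − 18²/68 = 38.2 | 6.18 | 2.0 | 4.2 |
| Week-2 minus day-1 pre-session | 2 × (25/2 + 25) = 75 | 8.66 | 2.8 | 4.2 |

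In the covariate row, the day-1 difference has variance 2 × (9 + 25) = 68 and its covariance with the week-2 difference is 2 × 9 = 18.

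**Step 4: chance of a significant difference (illustrative).** With a 5-point fall: averaged level 87% (79% if only pre or only post readings are used), week-2 pre-session unadjusted 98%. With a 3-point fall: 45% (39%) and 67%. The 2-hour change has no power against either.

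**Step 5: cost for a truly equal device.** At an assumed 3-point margin, the 2-hour change meets it about 98 to 99% of the time, a rate unaffected by any fall in level. The week-2 comparison would miss it about 19% of the time unadjusted, and about 43% if the day-1 value were simply subtracted.

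**The case against.** *The analysis is not tied to change scores.* Statistical Analysis works from pre and post values, and the Study Design null could be read as an FEV1 level at 2 hours. A level-based ANOVA would see a fall, and under the assumptions above would usually flag a 5-point one. This stands, and it rules out a stronger reading that a reader might infer: that the planned analysis is certain to miss a decline. The documents do not commit to a contrast. Aim 1's wording favours the change, and the averaged level shows about half the end-of-period loss.

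*There is no rule to pass.* A reader might also infer that a declining device would be declared non-inferior in nearly every trial. The documents give no margin or interval rule, and such a percentage follows from assuming equal session gains. Nor do they support the idea that retained secretions would give a weaker device a larger 2-hour gain.

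*Decline is monitored.* Testing is supervised by telemedicine, and the 10% criterion ends use of the experimental device. This is a real individual safeguard, so decline is not unwatched. But it applies to one device, does not enter the comparison, and stopped patients may leave it. It is also noisy: in a separate simulation (baseline mean 70, SD 15; slope SD 2 to 4; reading SD 2 to 3), 36 to 48% of patients crossed a 10% relative drop at some visit with a true 5-point fall, and 6 to 21% with none.

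*This is a pilot.* Statistical Analysis says it seeks a promising result, not a definitive one. That argues for a supportive comparison and against a mandatory second test; it does not remove the mismatch between Aim 1's conclusion and its measure.

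*Outpatient readings have limits.* With no washout stated, a fall on the PIAPD could carry into the standard-device period. No time of day is set, so a pre-session value may follow an earlier session. The first is why the period's day-1 value and the period and sequence terms are needed.

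**Conclusion.** The concern holds in a limited form. Aim 1's measure cancels a fall in level exactly, by algebra, and no listed endpoint compares FEV1 level between devices over the two weeks. The unspecified ANOVA might recover part of such a fall: about 2.4 of 5 points if it averages over sessions. The stopping criterion protects individuals but does not inform the comparison.

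The documents do not show that the PIAPD causes a decline, that the analysis would certainly miss one, or that a formal non-inferiority claim would follow. Every percentage and half-width rests on assumed SDs, visit days, drift shape and, where used, margin; they are illustrative only. Two weeks can show only short-term loss. This is a worthwhile, inexpensive improvement for the 40 outpatients.

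**What to change.** Pre-specify, as a key supportive outpatient analysis, the within-patient difference (PIAPD minus SACD) in mean week-2 pre-session FEV1, with each period's day-1 pre-session FEV1 as a covariate and with period and sequence terms. Use covariate adjustment, not simple subtraction, which widens the interval from about 2.0 to 2.8 points under the assumed SDs. State in advance, with a justification, what loss would be meaningful.

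Report the estimate and 95% CI beside the 2-hour change. If the interval does not exclude the meaningful loss, word the conclusion as concerning the acute 2-hour effect only. State also which contrast the repeated measures ANOVA tests.

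The change is to analysis wording and needs no new visits or readings. The cost is that the at-home claim becomes harder to reach: the supportive half-width is about 2 to 2.8 points against 1.4, and a truly equal device would often fall short of a tight margin. That is why the comparison is proposed as supportive and as a limit on wording, not as a second mandatory test.
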